Flare Study Protocol

PI: [name] [name]

Co-Investigators: [name], [name], and [name]

Research Staff: [name] BS, [name] BS, MS, [name] RN, CCRP

1. Purpose

Triamcinolone acetate (TA) and methylprednisolone acetate (MA) are standard of care (SOC) medications administered in shoulder injections depending upon Physician preference. The Physicians involved in the study have observed a difference in the rate of call backs following shoulder injection due to a reported increase in shoulder pain following the SOC injection. The purpose of this study is to compare the incidence of a flare reaction following administration of TA versus MA intra-articular glenohumeral and subacromial injections.

For the study, a flare reaction is defined as an increase of 2 or more from the baseline score on the visual analog score (VAS) in the first week following the shoulder injection.

2. Patient Enrollment

The study is a non-randomized, prospective, parallel-cohort study among subjects treated according to standard of care. Subjects will be approached for participation after electing to receive a corticosteroid injection in the glenohumeral joint or subacromial space as part of their SOC treatment plan. Three months was allotted for enrollment into the MA cohort followed by three months of enrollment into the TA cohort.

3. Inclusion Criteria

Any patient aged 18 to 95 who pursues a corticosteroid injection in the glenohumeral joint or subacromial space from one of three primary orthopedic Sports medicine or Shoulder specialists.

4. Exclusion Criteria

Patients will be excluded if they have received a corticosteroid injection in the previous three months.

5. Outcome Measures

The primary outcome measure is the incidence of a Flare reaction.

Secondary measures include VAS scores collected at the three-month time point. Another secondary measure is “treatment failure,” defined as a VAS score equal to or greater than a subject’s baseline VAS score. Subjects that proceed to another injection or surgery will also be defined as “treatment failures.”

6. Study Procedures

The consent form will be utilized to explain the study design to prospective subjects in a private room. Adequate time will be allotted for questions and answers with the study team. The pre-injection VAS will be administered in clinic. VAS scores for the week following injection will be obtained through a “home diary” data collection tool labeled with a subject code. After completing the “home diary” tool, patients will mail the stamped, form to the study administrator. The three-, six-, and twelve-month VAS scores will be collected by phone interviews with research staff.

7. Statistical Analysis Plan

Data will be collected and summarized by research staff. Advanced statistical analysis will be performed, including risk ratios for flare reaction development by cohort as well as standard and adjusted regression models.

8. Risk to Subjects

Subjects may experience tiresome or troublesome feelings while completing VAS scores through the “home diary” or phone interviews with research staff. Loss of confidentiality is a potential risk disclosed to subjects.

9. Benefit to Subjects

There are no direct benefits to subjects outside of the possible benefits of the SOC procedures being studied. However, the findings from the study may contribute to generalizable knowledge as assist with decision making practices at Campbell Clinic.

10. Subject Discontinuation

Subjects will not be contacted for subsequent study procedures if the subject withdraws from the study or if they are determined to have “failed” treatment.

11. Adverse Events

No incidental adverse events are expected as all study procedures are currently SOC.

12. Data Handling, Collection, and Record Keeping

Baseline VAS scores will be collected in clinic prior to injection. “Home diaries” will be mailed by subjects to research personnel in a manner that protects study confidentiality. Three-month VAS scores will be obtained through phone interviews conducted by research personnel. All data will be combined into a secure, password-protected electronic data capture (EDC) tool.

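### Does the plan need a rule for MA subjects who return for another injection while the TA cohort is enrolling?

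*Combined protocol and SAP*

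**What the plan says.** Section 2 (Patient Enrollment) sets the sequence: "Three months was allotted for enrollment into the MA cohort followed by three months of enrollment into the TA cohort". It also says who is invited: "Subjects will be approached for participation after electing to receive a corticosteroid injection in the glenohumeral joint or subacromial space". Section 3 admits any patient aged 18 to 95 who seeks such an injection from one of the three specialists. Section 4 has one exclusion: "Patients will be excluded if they have received a corticosteroid injection in the previous three months". None of these sections mentions earlier participation.

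Section 5 (Outcome Measures) adds to the definition of treatment failure: "Subjects that proceed to another injection or surgery will also be defined as" treatment failures. No time limit is attached. Section 10 (Subject Discontinuation) says: "Subjects will not be contacted for subsequent study procedures if the subject withdraws from the study or if they are determined to have" failed treatment.

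Section 7 plans "risk ratios for flare reaction development by cohort as well as standard and adjusted regression models". It names no covariates and does not say how a person with two records would be handled. Sections 6 and 12 describe the collection of VAS scores and no other named variable.

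**The concern.** The exclusion period and each enrollment window are all three months long. An MA subject therefore passes the exclusion just as TA enrollment is running. Sections 2 to 4 would have staff approach such a person for TA. Sections 5 and 10, read literally, make the same person a failure who is not to be contacted for further study procedures, and the TA diary and phone calls are study procedures. Staff could enroll or not enroll, and the text does not choose.

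Each choice has a possible cost in a non-randomized comparison:

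- **Returners enrolled.** Some people supply a record to both cohorts, so the cohorts are not independent.
- **Returners kept out.** TA loses people injected three to six months earlier as study subjects. MA keeps their counterparts, who were injected before the study began. If such patients flare at a different rate, the TA/MA risk ratio shifts, and the adjusted models could not correct this unless prior injection had been recorded.

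The route runs one way only. MA enrollment has closed by the time a TA subject could return.

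**Working it through.** The documents give no sample size, flare rate or repeat-injection rate, so there is no figure of the plan's own to reproduce. The check has three parts.

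**1. Is the route open?** Inputs from Sections 2 and 4: MA injection at month t (0 to 3), TA enrollment in months 3 to 6 (windows assumed back to back), and at least three months between injections. The subject is eligible from t + 3 to 6, which is (3 − t)/3 of the TA window: 100% at t = 0, 50% at t = 1.5 and 0% at t = 3. With uniform dates, about 50% of MA/TA date pairs are at least three months apart. The route exists.

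**2. How many could use it?** Assume t is uniform on 0 to 3 and a constant repeat rate h per month from injection. Count first repeats that fall more than three months after injection and before month 6:

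f = exp(−3h) × E[1 − exp(−h(3 − t))] = exp(−3h) × [1 − (1 − exp(−3h))/(3h)]

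At h = 0.10: 0.7408 × (1 − 0.2592/0.3) = 0.7408 × 0.1361 = 0.1008.

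**3. What would it do?**

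- *Returners enrolled.* Assume equal cohorts, equal flare risk, a share f of people in both cohorts and a within-person correlation of 0.3. The variance of the difference is then multiplied by 1 − 0.3f, so naive SE / true SE = 1/√(1 − 0.3f).
- *Returners kept out of TA.* Assume MA keeps an equal share f whose flare risk is k times that of others. The risk ratio is then multiplied by 1/(1 + f(k − 1)).

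| Assumed h per month | f | Naive/true SE | RR multiplier, k = 0.5 | RR multiplier, k = 2 |
|---|---|---|---|---|
| 1% | 0.0144 | 1.002 | 1.007 | 0.986 |
| 2% | 0.0277 | 1.004 | 1.014 | 0.973 |
| 5% | 0.0614 | 1.009 | 1.032 | 0.942 |
| 10% | 0.1008 | 1.015 | 1.053 | 0.908 |

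With k = 1 the risk ratio does not move.

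The shares f are not upper limits. Counting later repeats as well raises 10.1% to 11.1% at 10% per month. Section 2 does not say that the windows touch. With an assumed one-month gap, first repeats alone reach 2.2% at 1% per month and 15.0% at 10%. At f = 0.150 the same formulas give:

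- standard-error ratio: 1/√(1 − 0.045) = 1.023
- risk-ratio multiplier, k = 0.5: 1/0.925 = 1.081
- risk-ratio multiplier, k = 2: 1/1.15 = 0.870

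**Which reading applies?** Section 10 comes under a heading about discontinuation and speaks of people who are already subjects. The procedures that remain for them are the phone calls in Section 6. A returner is not being contacted under the MA enrollment. The person comes to clinic having elected an injection, is approached under Section 2 and goes through the consent process in Section 6. Section 10 sets no eligibility rule. A person can be a failure of the MA enrollment and a new TA subject at once, without the sections conflicting.

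Section 1 defines flare within the first week. Anyone eligible to return is at least three months past the MA injection, so their MA flare result is complete and joining TA cannot alter it.

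**The case for a change.** The strongest case for acting is that neither choice is neutral, that the comparison has no randomization to protect it, and that the remedy is cheap: one sentence on re-enrollment, one baseline field for prior injection and a line in Section 7. Section 4 already obliges staff to ask about recent injections, so recording the answer adds little work. Settling the rule before the cohorts are compared would also remove a choice made after the fact.

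Part of this stands. The text is silent on re-enrollment, and at the high end of the assumed rates, with returners kept out, the risk-ratio multiplier is not trivial (0.908, or 0.870 with a one-month gap, if flare risk doubles).

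But that result needs three things together: the less natural reading of Section 10, a high repeat rate, and a flare risk in returners well away from that of others. The documents support none of them and do not indicate the direction. Unnamed covariates are a general feature of Section 7 and not a defect peculiar to returners. Injection history is not unascertained either, since Section 4 requires a check of recent injections and Section 5 requires knowledge of later ones. What is missing is a named analysis field.

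**Conclusion.** No change follows. Sections 2 to 4 leave the route open, and Sections 5 and 10 do not clearly close it, but this is missing detail that study staff and analysts can fill sensibly. On the natural reading, the returner is a failure of the MA enrollment and a new TA subject. The cost is then a naive standard error 0.2% to 1.5% too large for first repeats with back-to-back windows, or 2.3% at the 15.0% share. That error is in the conservative direction, and clustering by person would correct almost nothing.

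A shift in the risk ratio arises only if returners are kept out. It is under 3% at 1% to 2% per month for flare risks halved or doubled, grows only at higher assumed rates, and is zero if flare risk is the same.

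All these sizes rest on assumed repeat rates, relative risks, a correlation of 0.3 and equal cohorts. Following the plan as written has not been shown to give a wrong answer, and writing the rule down has no demonstrated gain for the primary comparison.

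### Repeat recipients enter alongside first-time recipients, and no record of the earlier drug or flare is planned, so the flare risk ratio may carry a selection bias of unknown direction that the adjusted models cannot address

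*Combined protocol and SAP*

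**What the plan says.** Section 3 admits "Any patient aged 18 to 95 who pursues a corticosteroid injection in the glenohumeral joint or subacromial space" from one of three specialists and does not require the injection to be the patient's first. Section 4 holds the single exclusion: "Patients will be excluded if they have received a corticosteroid injection in the previous three months". It does not distinguish between drugs or injection sites, and older injections do not count.

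Section 1 describes the two drugs as "standard of care (SOC) medications administered in shoulder injections depending upon Physician preference". It gives no split between them. Section 2 sets the design: "The study is a non-randomized, prospective, parallel-cohort study among subjects treated according to standard of care". Patients are approached once they have chosen an injection, and cohorts are filled in sequence: "Three months was allotted for enrollment into the MA cohort followed by three months of enrollment into the TA cohort".

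Section 5 states: "The primary outcome measure is the incidence of a Flare reaction". Section 7 plans "risk ratios for flare reaction development by cohort" and, in the same sentence, standard and adjusted regression models. No covariate is named. The only measurements described in Sections 6 and 12 are VAS scores. Prior injection history is not listed for collection, stratification or adjustment.

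**The concern.** Someone who had a bad flare after an earlier injection may be less willing to have another. If so, repeat recipients who reach this study are a selected group: more of them tolerated what they had before. This is the usual prevalent-user problem, and it matters here because cohorts are not randomized and are enrolled in different periods.

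It can affect the comparison in two ways. First, if tolerance is specific to the drug and one drug was used more in the past, the cohort receiving that drug contains more people who already tolerated it. This can happen even when both cohorts have the same proportion of repeat recipients. Second, if tolerance covers both drugs, a difference in the proportion of repeat recipients between the MA and TA periods is enough.

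At stake is whether a flare risk ratio away from 1 reflects the drugs or the injection history of the people enrolled. Section 9 says the results may help guide practice at the clinic.

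**Working it through.** The plan states no sample size, flare rate, share of repeat recipients or past TA/MA split, so it has no figure to reproduce. Every input below is an assumption. The calculation also takes the enrolment period to set the drug and the past-drug mix to be the same in both cohorts.

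Notation, with a true TA/MA flare ratio of 1 and first-time risk set to 1:
- r: share of repeat recipients in each cohort
- f: share of those whose earlier drug was MA
- t: relative flare risk in a repeat recipient given the same drug
- c: relative flare risk in a repeat recipient given the other drug

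Observed TA/MA ratio = [(1−r) + r((1−f)t + f·c)] / [(1−r) + r(f·t + (1−f)c)].

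**Drug-specific tolerance (c = 1), r = 0.3**
- f = 0.7, t = 0.8: 0.982/0.958 = 1.03
- f = 0.7, t = 0.5: 0.955/0.895 = 1.07
- f = 0.9, t = 0.8: 0.994/0.946 = 1.05
- f = 0.9, t = 0.5: 0.985/0.865 = 1.14

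If TA was the more used drug, the ratio inverts: with t = 0.5, f = 0.3 gives 0.94 and f = 0.1 gives 0.88. Varying r from 0.1 to 0.5, with f from 0.7 to 0.9 and t from 0.8 to 0.5, widens the range to 1.01 to 1.26.

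**Where the bias vanishes**
- Even past use (f = 0.5): numerator and denominator are equal, ratio 1.00.
- Tolerance shared by both drugs (c = t) with equal r: 1.00 for any f.

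**Shared tolerance with unequal repeat shares.** With c = t = 0.5, 50% repeat recipients in the MA cohort and 30% in the TA cohort: (1 − 0.3×0.5)/(1 − 0.5×0.5) = 0.85/0.75 = 1.13.

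**Opposite mechanism.** If repeat recipients flare more on the same drug (t = 1.2, c = 1, r = 0.3), f = 0.7 gives 1.018/1.042 = 0.98 and f = 0.9 gives 1.006/1.054 = 0.95. The direction reverses.

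**Would a yes/no covariate for prior injection be enough?** Not under drug-specific tolerance. Suppose flare risk is 25% in anyone new to the drug and 10% in anyone who tolerated it before, half of each cohort are repeat recipients, and 80% of those last had TA.
- First-time recipients: MA/TA = 0.25/0.25 = 1.00.
- Repeat recipients: MA = 0.2×0.10 + 0.8×0.25 = 0.22; TA = 0.8×0.10 + 0.2×0.25 = 0.13; ratio 1.69.
- Equal strata pooled: (0.25 + 0.22)/(0.25 + 0.13) = 0.47/0.38 = 1.24, the same as the unadjusted 0.235/0.190.

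Classifying by none, same drug and other drug gives 0.25/0.25, 0.10/0.10 and 0.25/0.25, a ratio of 1.00 in each class. So the earlier drug has to be recorded, not only the fact of an earlier injection.

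**The case against.** A reader might infer that the design favours whichever drug the physicians used more, by something like the 1.24 in the last example. The documents do not support that. It requires that repeat recipients flare less, that earlier flarers stay away, that tolerance does not carry over between two corticosteroids, and that past use was uneven. None of these is stated. Section 1 says only that choice was "administered in shoulder injections depending upon Physician preference", and that call-back rates differed, which suggests both drugs were in use. Earlier injections may also have been given elsewhere.

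The 1.24 is also fragile:
- With half carry-over (other-drug repeat risk 17.5%), MA is 0.125 + 0.5×(0.2×0.10 + 0.8×0.175) = 0.205 and TA is 0.125 + 0.5×(0.8×0.10 + 0.2×0.175) = 0.1825, a ratio of 1.12. With full carry-over it is 1.00.
- A 10% risk in those who did not flare before implies that earlier flarers flare again at (0.25 − 0.75×0.10)/0.25 = 70%, and that all of them decline another injection. If half return, same-drug repeat risk is (0.075 + 0.0875)/0.875 = 18.6%. The ratio is then 1.09 with 50% repeat recipients and 1.05 with 30%.

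It is also fair to say that adjustment is planned, and that prior injection is one part of a wider gap, since no covariate is named.

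These objections remove any claim about direction and most of the size. They do not remove the gap itself: history that is not recorded cannot enter an adjusted model, and without it the bias can be neither signed nor bounded afterwards.

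**Conclusion.** The point holds as a gap in data collection and analysis, not as a demonstrated bias toward either drug. Eligibility mixes repeat and first-time recipients in a non-randomized, sequential comparison, and the plan records nothing that would separate them. Any resulting bias is probably modest: at 30% repeat recipients, with 70% to 90% having had the same earlier drug and a relative risk of 0.8 to 0.5 on re-use, it is about 1.03 to 1.14 or the reciprocal. It reaches about 1.26 only with half repeat recipients and very uneven past use, and it is zero under even past use or under shared tolerance with equal shares. All of this rests on assumed inputs. The change is worth making because it is cheap and must be made at baseline; the point does not undermine the study.

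**What to change.** When checking the three-month exclusion, also ask about any earlier corticosteroid injection, the drug (TA, MA, unknown) and whether pain flared afterwards. Ask about injections at any site, because tolerance of a drug could also have shown itself in another joint.

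In Section 7, name prior exposure (none, same drug, other drug, unknown) as a covariate in the adjusted model. Report the flare risk ratio in first-time recipients as a sensitivity analysis beside the all-subject ratio.

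Do not add a rule that attributes a difference to the drug only when the two ratios point the same way. With no drug effect, the first-time ratio falls on either side of 1 about equally often, so a false difference would pass about half the time or more. In a small subset the rule could also reject a true difference.

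The cost is two or three baseline questions and one extra analysis. The first-time estimate rests on fewer subjects and has a wider interval, and the earlier drug will sometimes be unknown or misrecalled, so some bias may remain after adjustment.

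### Does treatment failure need a stated VAS visit and a time limit for repeat injection or surgery before the cohorts can be compared?

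*Combined protocol and SAP*

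**What the plan says.** Section 5 (Outcome Measures) lists the secondary measures in order. The first is pain at a fixed time: "Secondary measures include VAS scores collected at the three-month time point". Treatment failure follows, "defined as a VAS score equal to or greater than a" subject's own baseline score. The procedure part comes last: "Subjects that proceed to another injection or surgery will also be defined as" failures. Neither part of the failure definition carries a date.

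Four other places bear on timing:

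- Section 2 (Patient Enrollment): "Three months was allotted for enrollment into the MA cohort followed by three months of enrollment into the TA cohort".
- Section 6 (Study Procedures): "The three-, six-, and twelve-month VAS scores will be collected by phone interviews with research staff".
- Section 10 (Subject Discontinuation) stops further contact with anyone who withdraws or is judged a failure.
- Section 12 (Data Handling, Collection, and Record Keeping) mentions only the first of the calls: "Three-month VAS scores will be obtained through phone interviews conducted by research personnel".

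Section 7 (Statistical Analysis Plan) names "risk ratios for flare reaction development by cohort as well as standard and adjusted regression models". It ties no time point or data cut-off to treatment failure.

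**The concern.** A cumulative yes/no outcome has no definite value until its time window is fixed. Here the procedure part is open-ended, and the VAS part could be read at three, six or twelve months. Flare, by contrast, has its window written into its definition in Section 1.

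Two things could be at stake. First, the proportion failing depends on the window, and a window chosen after the data are seen leaves room to pick the more striking result. Second, the cohorts are enrolled one after the other. If repeat procedures were counted up to a single date for everyone, for example in one chart review, MA subjects would have had about three months longer on average in which to have one. Part of any MA excess would then come from enrolment order, and a regression that ignored follow-up time would not remove it.

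**Working it through.** The documents give no failure rate, sample size or power, so there is no planned figure to reproduce. The check asks which windows the text supports, and what each does to the comparison when the drugs do not differ.

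**Readings and their support**

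- *Three months.* The sentence just before the definition is set at three months, and Section 12 mentions no other call.
- *Later scheduled calls, to twelve months.* Section 6 lists them, and Section 10's stop on contact after failure fits failure being judged at successive calls.
- *One calendar date for all.* No data cut, database lock or analysis date appears anywhere. Section 10 works subject by subject, which points away from this reading.
- *First-week diary scores.* Read literally, any VAS at or above baseline would count. A flare (a rise of 2 or more) would then itself be a failure, and Section 10 would end contact before the three-month VAS. An analyst would not adopt that reading.

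**Inputs (all assumed).** Twelve-month risk of a repeat procedure p = 10% to 30%. Risk of VAS failure at three months v = 10% to 25%. Both are the same in the two cohorts. Central case: p = 20%, v = 17%. The monthly rate is h = −ln(1 − p)/12; centrally, −ln(0.80)/12 = 0.0186. The two parts are taken as independent.

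**Window counted from each subject's own injection.** Failure by month m = 1 − (1 − v)·exp(−h·m).

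- m = 3: 1 − 0.83 × 0.9457 = 21.5% in each cohort, ratio 1.00.
- m = 12: 1 − 0.83 × 0.80 = 33.6% in each cohort, ratio 1.00.
- The smallest gap between the two windows is at p = 10%, v = 25%: 0.75 × (0.9740 − 0.90) = 5.6 points.
- The largest is at p = 30%, v = 10%: 0.90 × (0.9147 − 0.70) = 19.3 points.

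The m = 12 figure keeps the VAS part at three months and extends only the procedure part. It is not the full twelve-month reading, in which VAS at the later calls would count as well.

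**One calendar date for all (not in the documents).** Enrolment is taken as uniform, MA in months 0 to 3 and TA in months 3 to 6. For follow-up spread evenly from a to b months, the procedure risk is 1 − [exp(−h·a) − exp(−h·b)] / [h·(b − a)].

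| Cut | Follow-up, MA / TA (months) | Procedure risk, MA / TA | Composite, MA / TA | Ratio | Range of ratio |
|---|---|---|---|---|---|
| Month 9 (last three-month call) | 6–9 / 3–6 | 13.0% / 8.0% | 27.8% / 23.7% | 1.18 | 1.07 to 1.32 |
| Month 18 (last twelve-month call) | 15–18 / 12–15 | 26.4% / 22.2% | 38.9% / 35.4% | 1.10 | 1.05 to 1.13 |

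The composite is 1 − (1 − v)(1 − procedure risk). The ranges cover the assumed p and v. If VAS failures are re-treated at three times the rate of others, the ranges become 1.05 to 1.30 and 1.04 to 1.13. Every between-cohort distortion from the missing window comes from this reading.

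**The case for a change.** The strongest case for a change is that the gap is real and cheap to close. The three months in Section 5 belongs to the separate VAS measure; failure is introduced as a further one. Sections 6 and 12 differ on which calls are made. Even with three months accepted for the VAS part, the procedure part stays open, and the date and source of a repeat procedure are not listed among the data. A single chart review would be an ordinary way to find repeat procedures, and with staggered cohorts it could produce the imbalance in the table.

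The omission stands, and so does the point that the level of failure depends on the window. The step to bias does not. It needs a counting rule that nobody has written, applied by an analyst who ignores the three-month offset built into the design. The twelve-month reading is tenable but gives both cohorts equal time, so it changes the level and not the fairness of the comparison. The mismatch between Sections 6 and 12 does not alter the outcome list either, since Section 5 claims VAS as a secondary outcome at three months only. Wider additions, such as rules for missing failure status, best- and worst-case analyses or time-to-event methods, would correct no stated rule that gives a wrong answer.

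**Conclusion.** No change follows. Section 5 leaves out a detail of a secondary measure, and context supplies a sensible default: failure judged at three months from each subject's own injection, in the same way in both cohorts. On that reading, and on the later-call reading, equal true rates give a ratio of 1.00. The choice moves the absolute level, by 5.6 to 19.3 points under the assumed risks when only the procedure part is extended from three to twelve months. A report that states the window used makes that plain to its readers. A spurious MA excess of 1.05 to 1.32 needs a common calendar cut-off that the documents do not contain. All these figures rest on assumed risks, a constant procedure rate and, except where overlap is stated, independence of the two parts. The ratio of 1.00 under a fixed per-subject window depends on none of those values, only on the two cohorts having the same true risks.

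### Must Section 7 name the adjustment covariates and a single primary flare estimate before this non-randomised comparison is analysed?

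*Combined protocol and SAP*

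**What the plan says.** Section 5 fixes the outcome: "The primary outcome measure is the incidence of a Flare reaction". Section 1 defines it: "a flare reaction is defined as an increase of 2 or more from the baseline score", counted over the first week. Section 7 then plans analysis "including risk ratios for flare reaction development by cohort as well as standard and adjusted regression models". Neither Section 7 nor any other section names a covariate, a rule for choosing covariates, a model type, or which flare estimate leads.

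The setting is observational. Section 2 states: "The study is a non-randomized, prospective, parallel-cohort study among subjects treated according to standard of care". It also sets the order of enrolment: "Three months was allotted for enrollment into the MA cohort followed by three months of enrollment into the TA cohort". Section 1 covers "intra-articular glenohumeral and subacromial injections" together and says that drug choice ordinarily follows the treating physician's preference; Section 3 involves three specialists. On data, Section 12 says: "Baseline VAS scores will be collected in clinic prior to injection".

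**The concern.** In a non-randomised comparison the crude and adjusted risk ratios need not agree, so it matters which one is called the result. Three features sharpen the worry.

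- The study physicians "have observed a difference in the rate of call backs following shoulder injection", so there is a prior expectation that the drugs differ.
- Two injection sites are pooled, and their shares may differ between cohorts.
- Baseline VAS, a natural covariate, is also part of the flare definition. If the recorded baseline contains error, adjusting for it can add bias as well as remove it.

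If the lead estimate and its covariates were chosen after the data were seen, a reader could not tell whether the answer came from the drug or from the choice.

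**Working it through.** **What the text fixes.** The documents give no sample size, significance level, flare rate, VAS range or baseline variability, so the plan has no figure to reproduce. The outcome is fixed (Section 5), its threshold and window are fixed (Section 1), and one measure, the risk ratio by cohort, is expressly attached to it (Section 7). Open are the covariates and the ranking of estimates.

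**Assumed inputs for the illustrations.** Integer VAS 0-10; baseline SD 2; flare means highest week-one score minus recorded baseline is at least 2; Poisson model with a linear baseline term. Ratios are the lower-baseline cohort over the higher, from large simulated cohorts with no drug effect.

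**1. Does adjusting for baseline VAS help?** Take mean baselines of 6 and 6.5.

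- No baseline error, with the mean change depending on baseline at slopes -0.4, -0.2, 0, 0.2, 0.4: crude 1.17, 1.12, 1.06, 1.01, 0.97; adjusted about 1.00-1.01. Adjustment helps.
- Baseline error SD 0.4, 0.8, 1.0, 1.2: crude 1.05, 1.03, 1.03, 1.02; adjusted 0.97, 0.92, 0.90, 0.87. Adjustment helps at 0.4 and hurts from about 0.6.

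The two estimates can therefore fall on opposite sides of 1. Which is nearer the truth depends on an error SD that the documents do not give.

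**2. Is that gap visible at realistic precision?** Assume a 15% flare rate and 100 patients per cohort.

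SE of log risk ratio = sqrt(2 x (1 - 0.15) / (100 x 0.15)) = sqrt(0.1133) = 0.337.

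95% limits multiply and divide the ratio by exp(1.96 x 0.337) = 1.9.

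A crude ratio of 1.03 would have limits of roughly 0.5 and 2.0. The bias of either estimate is small against that.

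**3. What does free choice cost when there is no effect?** Balanced cohorts, 50-150 per cohort, 4000 simulated studies per setting, 5% test:

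| Rule | False positives |
|---|---|
| Crude alone | 3.1-5.0% |
| Smaller p of crude and baseline-adjusted | 4.2-6.4% |
| Smallest p over five covariate sets | 5.8-7.3% |

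**4. What does it cost when there is an effect?** Assume a 0.75-point drug shift (risk ratio 1.64-1.73 with balanced baselines). At 100 per cohort, crude and baseline-adjusted 5% verdicts differ in 7.5-9.2% of studies with balanced baselines and in 14.6-20.4% with a half-point imbalance in either direction. With the TA baseline lower (6 v 6.5), the figures are 10.1-11.3% at 50 per cohort and 17.2-21.2% at 150.

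**5. Injection site.** Assume flare rates of 20% and 12% by site and no drug effect.

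- Shares 55/45 v 45/55: (0.55 x 0.20 + 0.45 x 0.12) / (0.45 x 0.20 + 0.55 x 0.12) = 0.164 / 0.156 = 1.05.
- Shares 60/40 v 40/60: 0.168 / 0.152 = 1.11.

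The site-adjusted ratio is 1.00 in both.

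**6. Would one pre-named model be better?** Consider a site-adjusted primary with baseline VAS kept for a sensitivity analysis. In the no-error case it leaves the baseline bias in place: up to 1.17 at 6 v 6.5, and up to 1.37 at 6 v 7. It also omits physician, which Section 1 links to drug choice, and the documents do not say that site is captured as study data. Putting baseline VAS in the primary model reverses the trade: better with little baseline error, worse with more (adjusted 0.87-0.92 above). The documents cannot settle which applies.

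**The case for a change.** The best case for a change is that an outcome is not an estimate. Section 7 offers several analyses of flare and ranks none; listing risk ratios first does not make them primary, nor does it say whether they are crude. Adjustment is central to reading a non-randomised study, the investigators already expected a difference, Section 9 expects the findings to inform clinic practice, and naming the covariates would take only a few lines.

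Much of this stands. The covariates are indeed unnamed, and a ratio adjusted for an undeclared set is harder to interpret. What does not stand is the step from there to an unsafe result. The by-cohort risk ratio is planned in the same sentence as the adjusted models, so the comparison a sceptical reader would want is already part of the planned output. The call-back remark is the study's rationale, given without direction or size, and is not evidence of selective reporting. The 15-20% disagreement figure needs an assumed effect, an assumed imbalance and an assumed sample size together; about half of it is present even with balanced baselines.

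**Conclusion.** No change to the plan follows. This is missing detail that an analyst can fill sensibly: report the by-cohort flare risk ratio with the adjusted ratio beside it, state the covariates used, and keep the model small if flares are few. Injection site, treating physician and baseline VAS are the candidates the documents themselves suggest. Choosing among them is a trade-off with no demonstrated winner.

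Under the assumptions shown, choosing between the crude and baseline-adjusted p-values adds one or two percentage points to the false-positive rate. Disagreement under a real effect is more common, but it would be seen if both results are reported as Section 7 plans. The conclusion rests on that reporting; a report giving only one estimate would deserve the criticism. How far the estimates would differ in this study cannot be derived from the documents.

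The larger limit on interpretation is that the MA window precedes the TA window, so drug and enrolment period coincide. Naming covariates would not remove that.
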